a. Routine clinical practice: All potential patients seeking orthodontic treatment will have an initial consultation appointment with the orthodontist. At this appointment, the orthodontist will have an opportunity to assess patient needs/ expectations as well as conduct an examination to present viable treatment options to the patient. All patients will also have their teeth and gums scanned by an intraoral scanner. This information is sent to Align Technology whose proprietary software (ClinCheck) is used to design and engineer a sequential set of trays that would progressively move teeth to their ideal positions in the mouth. ClinCheck software also provides the quantitative estimate of the magnitude of tooth movement required (in tenths of mm) as well as its direction (in degrees). Together, this information is used to design the clear aligners.

b. Study related screening:

During this consultation appointment, the patients will be evaluated to see if they meet the stated exclusion criteria (missing teeth in maxillary arch; lateral incisors with pathology/ restorations, treatment plan include extractions, presence of anterior cross bite, need for maxillary lateral incisor extrusion) to screen out ineligible study participants.

All patients who do not meet the exclusion criteria will be considered potential study participants and will be informed of the study and requested to participate and consent obtained. Their teeth and gums will be scanned as indicated under routine clinical care and the final inclusion will be determined based on the report generated by ClinCheck (>0.3mm lateral incisor extrusion and <6mm crowding). The time gap between intraoral scanning and generation of ClinCheck is a few days and getting the consent for all non-excluded participants is proposed out of respect for patient/ doctor's time because it precludes a need for a separate appointment (just to get consent) and improves efficiency.

It will be explained to the patient that they could be excluded from the study if analysis of ClinCheck software data indicates their ineligibility (required lateral incisor extrusion <0.3mm and crowding >6mm). Such patients would be considered screening failures.

5. * Does this study have a separate protocol document (i.e. a multisite or sponsor's protocol) that contains a detailed description of the study's methodology?

Yes

No

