6. * Since a separate protocol document is not uploaded, describe the proposed research using language understandable to those IRB committee members whose expertise is not scientific. The description must include:

1. A statement explaining the study design

2. A detailed description of all the procedures that will be followed to carry out the study, preferably in sequential order, and in sufficient detail that the study's methods could be replicated

3. A description of all research measures/tests/interventions that will be used (if applicable)

See the help text for additional guidance

1.

Randomized Controlled Trial.

The biostatistician on the study team ([name]) will generate random sequence in blocks of 4 using a computer.

All study participants will be assigned a unique identifier (4 digit code) generated by the study team based on order of enrollment and the type of attachment. The key that links code to the patient will be stored in the PI's office computer that has restricted access (only to study personnel). The key will be destroyed when the study is completed.

2.

Members of the study team including residents, [name] will have a meeting prior to start of the study to calibrate on the screening criteria to determine eligibility as well as obtaining signatures and maintaining the consent documents. The team will also have a virtual meeting over zoom at least once a month to update on study progress.

All members of the study team will inform [name] when a study participant is recruited to the study through a secure email. [name] will then communicate the randomly assigned attachment design to the treating orthodontist based on the sequence generated by [name]. The treating orthodontist will then put this information as an order to Align Technology for the fabrication of the attachment trays and clear aligners.

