View Consent	Signed Consent by Participant Signed Assent by Child or Decisionally Impaired Adult Signed Parent/Guardian Permission or Legally Authorized Representative Consent Short Form Consent (limited applicability)	No Waivers Requested Waiver of Signature on Consent/Permission Forms (waiver of documentation of consent)	Other Principal Investigator Lead Student/Trainee Investigator (leading their own project) Co/Sub-Investigator Trainee/Student(working on project)	dental assistants who support the clinic operations	Consent process will start when treating orthodontists/residents deem the patient may be eligible based on established inclusion/exclusion criteria. Any member of the study team will present the research	All potential participants willfully seek care at any of the three study locations. These subjects choose to become patients after the initial consultation appointment. There is no pre-existing relationships	They would be given 2 weeks to make a decision. This is a short term study that will last a maximum of 6 months. In the unlikely situation that the participant enters adulthood at any stage of the study (while actively on the first series of aligners or during data analysis), we will re-consent

study in detail in a semi private room in the treating orthodontic clinic to potential participants. If the patient agrees to participate in the study, the consent document will be presented and their signature obtained. If the participant is not an adult, the conversation will include the parent/ legal guardian and their signatures obtained. Children assent will be obtained when appropriate

between the treating resident / orthodontist and the potential patient. In this sense, study participants are no different from any other patient. In any case, the study team will make it clear to the potential participant that the participation is completely voluntary and non-participation will not affect the intended treatment in any way.

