The study is a 4-arm randomized trial. Subjects will be screened for eligibility based on inclusion/ exclusion criteria. Once informed consent is obtained, the participants will be randomly assigned to one of the four attachment designs. The biostatistician on the study team ([name]) will generate random sequence using a computer. The randomization will be in block of 4 and the list will be provided to the study team.

All study participants will be assigned a unique identifier (4 digit code) generated by the study team based on order of enrollment and whether they received horizontal, incisally bevelled, gingivally bevelled or optimized attachments. This key that links code to the patient will be stored in the PI's office computer that has restricted access (only to study personnel). The key will be destroyed when the all participants complete their second scan (data collection is complete).

All data records used for analysis will have this assigned code without any identifying information. This will minimize the amount of recontacting needed for children who turn 18 during data analysis stage.

ID: HM20021396

View: SF2 - Data Retention

Data Retention

1. * **Select all of the ways that individually identifiable information obtained during pre-screening and/or screening will be handled for individuals who DO NOT qualify for the study:**
 - Immediately destroy the information and identifiers (no data collected)
 - Immediately destroy the identifiers connected with the data (anonymization)
 - Store until the end of study & then destroy
 - Use as "screening failure" data by members of the study team
 - Provide to others outside of the research team (with the participant's permission)
 - Request permission from participant to maintain and use the identifiable information
 - Other
 - N/A - study does not require screening procedures**
2. * **Will participants be able to withdraw their data (paper, electronic, or specimens) from the study (e.g. ask that it be destroyed or returned) if they no longer wish to participate? (FDA-regulated studies should select No - see help text)**
 - Yes
 - No**
3. * **What will happen to the research materials (e.g. data, specimens, documents, etc.) when the research has been completed?**
 - Stored indefinitely with identifiers removed
 - Stored indefinitely with identifiers attached

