- Principal Investigator
- Co/Sub-Investigator
- Medical or Psychological Responsible Investigator
- Lead Student/Trainee Investigator (leading their own project)
- Research Coordinator
- Research Nurse
- Consultant
- Research Assistant

-
- Pharmacist
-
- Statistician
-
- Regulatory Coordinator
-
- Trainee/Student(working on project)
-
- Other
-
- N/A: Requesting Waiver of Consent

5. If Other is selected, explain:

dental assistants who support the clinic operations

6. * Describe the consent procedures used for this group. Include when, where, and how consent / assent will be obtained both initially and, if applicable, during ongoing participation in the study:

Consent process will start when treating orthodontists/ residents deem the patient may be eligible based on established inclusion/ exclusion criteria. Any member of the study team will present the research study in detail in a semi private room in the treating orthodontic clinic to potential participants. If the patient agrees to participate in the study, the consent document will be presented and their signature obtained. If the participant is not an adult, the conversation will include the parent/ legal guardian and their signatures obtained. Children assent will be obtained when appropriate

7. * Describe the process for minimizing any potential perception of undue influence to participate when there is a pre-existing relationship between the participant and the researcher (e.g. treatment provider/patient; instructor/student; supervisor/employee, etc.):

All potential participants will seek orthodontic care at any of the three study locations. These subjects choose to become patients after the initial consultation appointment. There is no pre-existing relationships between the treating resident / orthodontist and the potential patient. In this sense, study participants are no different from any other patient. In any case, the study team will make it clear to the potential participant that the participation is completely voluntary and non-participation will not affect the intended treatment in any way.

8. * How much time will participants be given to make a decision:

They would be given 2 weeks to make a decision.

9. If applicable, describe the procedures for consenting children upon entering adulthood or participants who are no longer decisionally impaired:

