This is a short term study that will last a maximum of 6 months. In the unlikely situation that the participant enters adulthood at any stage of the study (while actively on the first series of aligners or during data analysis), we will re-consent him/her using the adult consent document. Even though the study itself lasts only 6 months, the comprehensive orthodontic treatment would take much longer (12-18 months). In a vast majority of cases, incisor correction is done at the start and we expect all data analysis to be completed within a few months after the second scan. There are 2 possibilities when the issue of re-consenting arise:

- a. If the participants turns 18 while they are still on aligner therapy (irrespective of whether they are on initial series or beyond): In these cases, the study team will have an opportunity to see the participant in person for routine follow-up and will re-consent in person
- b. In the rare instance where the patients are off aligner therapy when data analysis is still in progress, the study team will reach out to the participant over phone and will seek re-consenting. We have checked the box for waiver of documentation of re-consent.

ID: HM20021396

View: SF_IRB_StudyLocation_NonVCUSitesDetails

Non-VCU Site Details

1. * Name of institution or site:

[name] Orthodontics, [name]

2. * Provide a description of the institution's or site's role in the research and what study activities they will be performing:

[name] owns and runs the exclusive orthodontic practice in Richmond. He is also an adjunct faculty in the Department of Orthodontics at VCU SoD.

[name] will identify potential participants and recruit them in the study if the patient meets the inclusion/ exclusion criteria and sign the informed consent. He will inform the PI once the consent is obtained. The PI will then relay the randomized assignment of the attachment design to [name]. The patient will be treated in [name] office and all necessary data (intraoral scans and ClinCheck) will be shared with the PI through a HIPAA-secure portal maintained by Align Technology. All patient information (including demographic information and photos) are maintained in the cloud and can be accessed only by a Invisalign-registered doctor or staff. This access is restricted by an username and password.

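### The block-of-4 list is said to go to the study team, which recruits; the order of assignment and ClinCheck eligibility is not explicit, and the analysis ID is based on the arm

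*Combined protocol and SAP*

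**What the plan says.** **Who has the list.** Data Confidentiality and Storage, question 9, states: "The randomization will be in block of 4 and the list will be provided to the study team". Consent Groups, question 6, states: "Any member of the study team will present the research study in detail in a semi private room". Study Procedures, question 6, gives a narrower route: recruiters notify one person by secure email, and that person "will then communicate the randomly assigned attachment design to the treating orthodontist". Non-VCU Site Details, question 2, has the same structure for a private practice: "He will inform the PI once the consent is obtained", followed by "The PI will then relay the randomized assignment of the attachment design to" the treating orthodontist. In the Consent Process table, the roles that obtain consent read in part: "Principal Investigator Lead Student/Trainee Investigator (leading their own project".

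**When assignment happens.** Data Confidentiality and Storage, question 9, states: "Once informed consent is obtained, the participants will be randomly assigned to one of the four attachment designs". Study Procedures, question 4, takes consent from everyone not excluded at the consultation, then scans, and then "the final inclusion will be determined based on the report generated by ClinCheck", a few days later.

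**What the ID contains.** Study Procedures, question 6, and Data Confidentiality and Storage, question 9, build a 4-digit participant code from enrolment order and attachment type. The latter puts that code on every record used for analysis.

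**The concern.** Concealment depends on the person who decides whether to approach or enrol a patient not knowing the next assignment. Taken literally, the list sentence and the consent sentence together give the future sequence to people who recruit. The incentive is plausible here. The background section says that experts favour different designs, and Study Procedures, question 8, says that patients outside the trial receive the attachment their orthodontist chooses. A clinician who foresees the arm therefore has another route for that patient.

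Timing matters for a similar reason. If the arm is known before ClinCheck eligibility is final, it could influence who becomes a screening failure.

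The ID raises a separate matter of assessment. Whoever superimposes the models or runs the analysis could read the arm from the record label. Bias from selection or from unmasked assessment is hard to detect or correct afterwards.

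**Working it through.** The plan gives no figure for predictability, and its power calculation does not bear on this point, so there is nothing to reproduce first.

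**Inputs.** Four arms and blocks of 4 (Study Procedures, question 6; Data Confidentiality and Storage, question 9), so each arm is taken to appear once per block. Target of 80 teeth, at least 20 per arm (Study Procedures, question 6), giving 80/4 = 20 blocks. Three locations (Study Procedures, question 4). Both incisors of a patient may qualify (Compensation, question 1); the share of such patients is not given.

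**1. Recruiter holds the list.** All 80 of 80 assignments are known in advance.

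**2. No list, but block position and all earlier assignments known; one tooth per patient.** The chance of a correct guess is 1/4, 1/3, 1/2 and 1 at positions 1 to 4.
- Mean: (1/4 + 1/3 + 1/2 + 1)/4 = 0.521, or 80 × 0.521 = 41.7 correct guesses.
- By chance: 80 × 0.25 = 20.
- The last slot of each block, 20 of 80, is certain.

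**3. Same knowledge, every patient contributing two teeth, both guessed before enrolment.** (0.25 + 0.25 + 0.5 + 0.5)/4 = 0.375. Mixed shares fall between 0.375 and 0.521.

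**4. Recruiter sees only a fraction p of earlier assignments; one tooth per patient, position known.** At position k the number seen, s, is Binomial(k − 1, p), and the chance of a correct guess is 1/(4 − s).
- p = 1/3 (assumes three equal sites): 0.250, 0.278, 0.315, 0.370; mean 0.303.
- p = 1/2: 0.250, 0.292, 0.354, 0.469; mean 0.341.

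**5. Timing, with the passages set side by side.**
- Pointing to assignment after ClinCheck: Data Confidentiality and Storage, question 9, mentions screening against the criteria before consent and assignment. Non-VCU Site Details, question 2, makes recruitment depend on the criteria as well as consent, and one criterion is set by ClinCheck. Study Procedures, question 4, calls ClinCheck-ineligible patients screening failures, and Risks, question 5, treats the ClinCheck check as part of screening. Randomization by tooth also presupposes knowing which teeth qualify.
- Pointing to assignment before ClinCheck: the stated trigger in two places is consent, and Study Procedures, question 4, puts consent before the ClinCheck report. Risks, question 5, lists ClinCheck ineligibility as a reason to withdraw a participant.
- No available sentence settles the order.

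**6. The 0.3 mm boundary.** Study Population, questions 4 and 5, admit a tooth at exactly 0.3 mm, and so does the failure rule at the end of Study Procedures, question 4. An earlier sentence in that same answer, and Secondary Data/Specimen Details, question 1, require more than 0.3 mm. ClinCheck reports in tenths of a millimetre, so a reading of exactly 0.3 can occur and is treated both ways.

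**The case against.** The strongest reply is that Study Procedures, question 6, is the operating procedure, and a one-person relay would be pointless if every recruiter held the list. The contrary sentence answers a question about subject-ID coding and may be loosely worded. The relayer's name in Study Procedures is blacked out, so the plan may be clearer than it looks. This is fair, and it rules out the inference that recruiters will certainly see the sequence. It does not remove the conflict: no available page restricts the list, and at the private practice the relayer is a person who may obtain consent.

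On timing, a reader might infer that the plan intends to randomize ineligible patients. The documents do not support that, because several sentences place screening first. What remains is a missing explicit order. The 0.3 mm discrepancy affects only a tooth at exactly that value.

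On predictability, 52% needs full knowledge of a three-location sequence. With a third of assignments seen, the figure is about 30%, close to chance.

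On the ID, a reader might infer that one code cannot describe a patient with two different attachments, or that it makes masking impossible. Neither follows. The layout of the four digits is not given, and files can be relabelled before measurement. No masking is promised, and GeoMagic calculates the movement values, which limits the room for assessor influence.

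**Conclusion.** The concern holds as a conflict in the stated rules with a cheap remedy. It does not show that allocation has been or will be compromised.

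- **List custody.** The text as written exposes the sequence to recruiters; the relay is a partial safeguard that does not restrict the list. The exposure is all 80 assignments if recruiters hold the list. Otherwise it is at most 52% correct guesses against 25%, under the assumptions of one tooth per patient, one unstratified list, known block position and all earlier assignments seen. Two-tooth patients or site-limited knowledge lower it.
- **Timing.** Assignment after ClinCheck is a reasonable reading, but the stated trigger is consent, so the order needs to be explicit.
- **ID.** Anyone who knows the scheme can read the arm while superimposing or analysing.

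The documents do not show how large any resulting bias would be. Statements about what the plan lacks cover the available pages only, since some were removed. This should be corrected, with medium confidence.

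**What to change.** 1. In Data Confidentiality and Storage, question 9, delete the clause giving the list to the study team. State that an existing team member who neither recruits nor obtains consent holds it. The biostatistician, who already generates the sequence, is one candidate: no statistician appears among the consent roles, though the personnel pages are not available to confirm this.
2. There, and in Study Procedures, question 6, and Non-VCU Site Details, question 2, state that each tooth's assignment (both together for a two-tooth patient) is released only after that tooth's ClinCheck eligibility is recorded. The relay to the treating orthodontist can stay. Reconcile the 0.3 mm wording across Study Population, Study Procedures and Secondary Data/Specimen Details.
3. Make the ID an enrolment number plus tooth side, keep the arm in a separate file, and do the superimposition under that ID. If the list holder also runs the analysis, have someone else recode the arms to neutral labels first, or state that the analysis is unmasked.

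**Cost.** The list holder answers up to 80 release requests, and IDs already issued need one relabelling pass. Waiting adds no visit, since ClinCheck already follows the scan by a few days. The masking gain may be partial, because attachments can be visible on the second scan and the software calculates the values.

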Both independent investigators will complete the CITI training and submit the documentation of completion to the PI prior to enrolling participants in their offices.

4. * Upload a CV or Biosketch for the PI, Medically/Psychologically Responsible Investigators and the lead Student/Trainee Investigators. Do not upload CVs or Biosketches for other individuals.

ID: HM20021396

View: SF2 - Conflict of Interest

Conflict of Interest

The PI should ask the questions on this page of all research personnel who are engaged in the research, including subrecipient investigators and personnel.

1. * To the best of your knowledge, do you (as PI) or any other engaged individual have a financial interest related to this study?

Financial interests include utilizing your licensed intellectual property in the study; serving as a paid consultant, or advisory board member, or officer/director with a related entity; and equity or business ownership in a company that is related to this project.

Yes
 No

2. * To the best of your knowledge, do you (as PI) or any other engaged individual have a non-financial interest related to this study?

*Non-financial interests could include such things as:
- utilizing your unlicensed intellectual property in the study,*

- serving as an unpaid advisory board member or officer/director with a related entity, and
- equity or business ownership in a company that has yet to make a profit and is related to this project
- conflicts of time/effort,
- personal and professional relationships/affiliations,
- intellectual passions or personal beliefs
- other factors that could create bias in the study

Yes

No

3. Describe any institutional conflict of interest that you or any member of the research team are aware of that pertains to this research:

An institutional conflict of interest is a situation in which financial interests of the University or University leadership may affect research activities at VCU.

ID: HM20021396

View: SF2 - Other VCU Requirementsv2

Other VCU Requirements

This page asks questions on behalf of other ancillary offices, committees and departments at VCU regarding institutional requirements that could apply to this research. In some cases, these requirements could also impact the consent process or other aspects of the IRB's review.

Based upon answers provided earlier in this form, certain ancillary sections below may not have questions displayed if those requirements are not applicable to this study.

1. Cost Coverage Analysis

Information on coverage analysis requirements and processes can be found through VCU's Clinical Research Compliance Program at https://research.vcu.edu/compliance_program/research_coverage.htm

1. * VCU requires that all clinical research studies be evaluated to determine if a Coverage Analysis is required. Has your study been evaluated by an institutionally designated Coverage Analysis Specialist?

Yes

No

Not Applicable

2. ClinicalTrials.gov Program & OnCore

For guidance, see <https://cctr.vcu.edu/support/consultation/clinical-trials-gov/> or email [contact]

1. * Is this a Clinical Trial?

Yes No

2. * ThePI acknowledges awareness of the following requirements for posting clinical trial consent forms:

- Each clinical trial under the 2018 Common Rule that is conducted or supported by a Federal department or agency must post one IRB-approved consent form that was used to enroll subjects on a publicly available Federal website [45 CFR 46.116(h)].
- When engaged in multi-site research, the VCU PI is responsible for confirming with the lead site who is responsible for posting the informed consent form.
- When VCU is the lead site, the VCU PI is responsible for posting the informed consent form (unless the federal department or agency will post it).

Yes No

3. Community Engagement

For more information, see <https://community.vcu.edu/>

1. * Is there a community partner in this research study?

Yes No

4. Family Educational Rights and Privacy Act (FERPA) Requirements

For guidance, see <https://rar.vcu.edu/records/family-educational-rights-and-privacy-act/>

1. * Does this study involve obtaining information from VCU students' educational records (see help text)?

 Yes No

5. General Data Protection Regulation (GDPR) Requirements

Contact the VCU Research Data Privacy Office with questions about GDPR requirements:
https://research.vcu.edu/data_privacy

1. * Does this study involve the VCU site, or any sites under the VCU IRB's oversight, obtaining data in, or from, the European Economic Area? (see Help Text for list of countries included in the EEA)

 Yes No

6. Information Security

For guidance, see <https://ts.vcu.edu/askit/essential-computing/information-security/>

1. * Using the VCU Data Classification Tool, please determine the appropriate data classification category for the data that will be collected or used in this research.

Note: if the data falls into Category 1, a data security management plan is required by University Information Security Office.

See help text for information on accessing the VCU Data Classification Tool, and for information on creating a data security management plan.

- Category 1: all data that require breach notifications in the event of improper release, including personally identifiable information covered by HIPAA and Commonwealth of Virginia regulations.
- Category 2: all proprietary data that if improperly released has the potential to cause harm to the institution, its mission or its reputation that do not require breach notifications.

2. * I confirm use of the VCU Data Classification Tool in determining the data classification category selected in Question 1:

 Yes No

7. Massey Cancer Center Protocol Review and Monitoring Committee (PRMC)

For guidance, see <https://www.massey.vcu.edu/research/protocol-review/>

1. * Does this study involve any of the following?
- Research involving patients with cancer, their families or their health care providers
 - Research involving cancer screening, diagnosis or prevention
 - Secondary data collected from cancer patients or their medical records
 - Cancer-related surveys (e.g., attitudes about risk, prevention and treatment) of the general population

 Yes No

8. VCU Health Department of Patient Centered Services

1. * Does your study involve a satisfaction survey administered to VCUHS patients (*See Help Text):

 Yes

- No
 Not Applicable

9. VCU Faculty-Held IND or IDE

For guidance, see <http://go.vcu.edu/indide>

10. VCU Health System locations

1. * Will research activities occur in patient care areas of the VCU Health System (including at CHoR, Community Memorial Hospital, VCU Medical Center and Massey Cancer Center)?

- Yes
 No

11. VCUHS Department of Pathology

Learn more about requesting and establishing an account with Pathology here: See <https://pathology.vcu.edu/research-services/>

12. VCU Institutional Biosafety Committee (IBC)

To contact the Biosafety Office see their website at: <https://research.vcu.edu/ibc>

1. * Does this project involve the use of Bio-Hazardous Substances such as gene transfer, use of organisms or their products, biological toxins, and/or viruses? See the IBC website for more information about when review is required.

- Yes
 No

2. * Does this project involve recombinant DNA (rDNA) and/or synthetic nucleic acids?

- Yes
 No

13. VCU Radiation Safety Committee (RSC)

To contact the Radiation Safety Section see their website at: <https://research.vcu.edu/rsc>

1. * Does this study involve radiation exposure and/or scans involving radiation (e.g.: PET, MRA, CT, DXA, nuclear medicine, etc.)?

- Yes
 No

14. Virginia-Stem Cell Research Oversight (SCRO)

For guidance, contact the Office of Research Integrity and Ethics (ORIE) at: [contact]

1. * Does this study involve stem cells?

- Yes
 No

15. VCU Scientific Review Committee (SRC)

For guidance, see <https://ctr.vcu.edu/support/consultation/scientific-review-committee/>

1. * Has this human subjects protocol (not the grant application) already been reviewed by the funder of a sponsored project (e.g. a federal, state or non-profit funding sponsor)?

- Yes
 No

16. Upload any documents requested in the questions above:

ID: HM20021396

View: SF2 - HIPAA

HIPAA

HIPAA Privacy Board Requirements

For guidance, see <https://www.vcuhealth.org/our-story/who-we-are/compliance-services/compliance-services>

1. * **Select the source of the Individually Identifiable Health Information. See help text for definitions.**
 - PHI associated with or derived from (i.e. obtained from or entered into) VCU Health medical records or VCU Dental Care records**
 - Research Health Information (RHI) created or received by a study and kept solely in study records (e.g. self reported or the result of research tests and not entered into health records)
2. * **Summarize the types of health information that will be obtained or used in this research. Do not describe only the identifiers that you will collect or use during the study.**
EHR of potential study participants will be accessed to screen for eligibility. Specifically, results of comprehensive oral exam, x-rays/ images, treatment plans and patient visit notes will be accessed.
3. * **Describe the source(s) of the protected health information (e.g. which clinical databases):**
The electronic health record system used in School of Dentistry (axiUm).
4. * **Does the PI certify that this study's access to and use of the protected health information is limited to the minimum amount necessary to be able to effectively conduct the research?**
 Yes No
5. * **Select all pathways this research will employ to use or access PHI (selections will branch):**
 - De-Identified Data (none of the 18 identifiers are recorded or associated with the research data)
 - Limited Data Set
 - Waiver of Authorization
 - Partial Waiver of Authorization (temporary waiver for recruitment purposes and/or waiver of some elements of Authorization)**
 - Signed Authorization Combined with Consent Form**
 - Signed Authorization as Stand-Alone Form

ID: HM20021396

View: SF2 - Partial Waiver of Authorization

Partial Waiver of Authorization

1. * **Select the purpose for requesting the partial waiver of authorization:**
 - Identify possible participants to recruit for the study**
 - Waive some elements of authorization (such as signature)
2. * **Explain how the partial waiver of authorization poses no greater than minimal risk to participants' privacy: (Alternative question phrasing: How do the risk(s) of this use of identifiable health information compare to the risks to privacy a person might reasonably experience in normal everyday life?).**
The partial waiver is intended to screen and identify potential participants. Upon subject identification, full, signed authorization prior to study enrollment.
3. * **If you selected "Identify possible participants to recruit" above, describe when will the 18 HIPAA identifiers be destroyed for those who do not eventually enroll in the study?**
 - Following Participant Contact
 - Upon Reaching Study Accrual Objectives**

Other

4. * Other than the PI and research personnel identified in this research application, who else will have access to the Protected Health Information?

No additional personnel will have access to the PHI

5. * Explain why the study cannot practicably be conducted without the partial waiver of authorization: (Alternative question phrasing: Why is this partial waiver necessary to make the study achievable or viable?)

All study participants need to fit specific inclusion/ exclusion criteria as detailed earlier. There is no way to assess patient eligibility without this screening/ consultation appointment. The partial waiver of authorization provides the mechanism to access the PHI which is pivotal for screening and recruiting research study participants

6. * In applying for a partial waiver of authorization, the PI agrees to the following:

A) The identifiers used for this research study will not be used for any other purpose or disclosed to any other person or entity (aside from members of the research team identified in this application), except as required by law.

B) If at any time I want to reuse this information for other purposes or disclose the information to other individuals, I will seek approval from the IRB/Privacy Board.

C) I will comply with VCU HIPAA policies and procedures and to the use and disclosure restrictions described above.

D) I assume responsibility for all uses and disclosures of the PHI by members of my study team.

Yes

No

ID: HM20021396

View: SF2 - Institutional Requirements Complete

Institutional Requirements Complete

Protocol Progress:

? INITIAL SETUP

? BACKGROUND, RATIONALE & GOALS

? RESEARCH PLAN

? CONSENT PLAN

? RISKS, PRIVACY & CONFIDENTIALITY

? POPULATIONS WITH SPECIAL CONSIDERATIONS

? INSTITUTIONAL REQUIREMENTS

? DOCUMENTS

Click Continue below to go to the next section

ID: HM20021396

View: SF2 - Documents

Documents

1. Upload any documents that the VCU IRB will need to conduct a review of this submission:

A list of potential documents is given in the help text.

NOTE: The delete function should only be used if an incorrect document is uploaded or added to the system AND that document has not been reviewed and approved by the IRB. Do NOT delete documents that the IRB previously reviewed and approved.

Once you have uploaded a document to RAMS-IRB, any changes to that document (i.e. different versions of the same document) should be added to the IRB submission by using the Update button. To provide updated documents, follow these steps:

- Click the Update button located to the left of the document to be updated.

- In the Add Document window, click the Choose File or Browse button, select the file you are adding, and

click on the Open button.

- Click OK to close the Add Document window, and the system will upload the revised document. RAMS-IRB will automatically provide a version number for the document.

To access previous versions of a document in RAMS-IRB you must use the History link associated with the document.

- Click the View or Update button located to the left of the document you wish to access.

- In the Add/View Document window, click the "History" hyperlink located to the right of the file name.

- A separate window will open that shows all versions of the document that have been added to RAMS-IRB. Click on any file name to download and view the document.

	Document Name	Document	Version	Date Modified	Uploaded By	Type	Approved
